To evaluate the effects of intracanal cryotherapy and two intracanal medicaments (calcium hydroxide and metformin) on postoperative spontaneous and percussion pain in mandibular premolar teeth with symptomatic apical periodontitis.

Null hypothesis: No significant difference exists in postoperative pain among the study groups.

3. Study Design

- Randomized, double-blind, 2×2 factorial clinical trial
 - Parallel-group design with four groups:
 1. Calcium hydroxide
 2. Metformin
 3. Cryotherapy + calcium hydroxide
 4. Cryotherapy + metformin
 - Duration: Postoperative follow-up for 7 days
-

4. Ethical Approval

- Approved by Hamidiye Clinical Research Ethics Committee, University of Health Sciences (Approval No.: 13.02.2023–15184)
 - Written informed consent obtained from all participants
-

5. Sample Size Calculation

- Software: G*Power 3.1
 - Effect size: $f = 0.40$
 - Power: 0.90
 - Significance level: $\alpha = 0.05$
 - Total sample: 80 patients (20 per group)
-

6. Participants

Inclusion Criteria:

1. Systemically healthy
2. Mandibular premolars with pulpal necrosis requiring root canal treatment
3. Periapical index score 0–2
4. Age 18–70 years
5. Able to understand and complete VAS assessments
6. Provided written informed consent

Exclusion Criteria:

1. Systemic disease or pregnancy
 2. Analgesic use within 24 hours prior to treatment
 3. Severe bruxism
 4. Acute apical abscess or swelling
 5. Periodontal pocket >5 mm or tooth mobility $>$ grade 1
 6. Unrestorable teeth
 7. Vital pulpal tissue or immature apices
 8. Radiographic evidence of root resorption, root fracture, perforation, or canal calcification
-

7. Randomization and Blinding

- Random sequence generated using Randomizer.org
 - Allocation concealment by independent investigator
 - Operator and patients blinded to:
 - Type of intracanal medicament
 - Presence/absence of cryotherapy
-

8. Intervention

Root Canal Treatment Protocol:

- Local anesthesia: Articaine hydrochloride + epinephrine
- Rubber dam isolation
- Access cavity preparation
- Working length determination: Electronic apex locator + radiographic confirmation
- Canal instrumentation: ISO #40 apical size
- Irrigation:
 - 2 mL 5.25% NaOCl per instrument change
 - 5 mL 17% EDTA
 - Final rinse: 10 mL sterile saline over 5 min (4 °C in cryotherapy groups; 20 °C otherwise)
- Drying with sterile paper points

Intracanal Medicament Placement:

- Powder-to-liquid ratio: 1:1
- Lentulo spiral, 800 rpm, 20 s, 2 mm short of working length
- Groups 1 & 3: Calcium hydroxide
- Groups 2 & 4: Metformin
- Temporary restoration of access cavity

Cryotherapy Application:

- Final irrigation with sterile saline at 4 °C for cryotherapy groups (Groups 3 & 4)
-

9. Outcome Measures

Primary Outcome:

- Postoperative spontaneous pain (VAS 0–100 mm), recorded pre-op and daily for 7 days

Secondary Outcome:

- Percussion pain (VAS 0–100 mm), assessed pre-op and post-op
-

10. Statistical Analysis

- Software: R Statistical Software
- Significance: $\alpha = 0.05$

Analysis Plan:

- Spontaneous pain: Linear mixed-effects model for repeated measures
 - Percussion pain: ANCOVA with preoperative pain as covariate
 - Fixed effects: Time, cryotherapy, medicament type, and cryotherapy \times medicament interaction
 - Random effect: Patient
-

11. Data Management

- Pain levels recorded by patients before any analgesic use
 - Confidentiality maintained; individual patient data not shared publicly
-

12. Follow-Up

- Pain assessment: Days 1–7 postoperatively
 - No long-term follow-up in current study; suggested for future research
-

13. Expected Results

- Intracanal cryotherapy expected to reduce postoperative pain
 - Metformin effect on short-term pain expected to be comparable to calcium hydroxide
 - No significant interaction anticipated between cryotherapy and medicament type
-

14. Strengths and Limitations**Strengths:**

- Randomized, double-blind, factorial design
- Standardized treatment protocol
- Appropriate statistical methods for repeated measures

Limitations:

- Short follow-up (7 days)
- Single-center study
- Subjective pain assessment (VAS)

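### The primary spontaneous-pain model omits the pre-operative score as a covariate and does not say whether that score is an outcome row

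*Combined protocol and SAP*

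**What the plan says.** Section 9 defines the primary outcome as "Postoperative spontaneous pain (VAS 0–100 mm), recorded pre-op and daily for 7 days". Section 10 assigns it "Spontaneous pain: Linear mixed-effects model for repeated measures". The terms listed there are "Fixed effects: Time, cryotherapy, medicament type, and cryotherapy" by medicament interaction, with patient as the random effect. Neither a pre-operative term nor a time-by-treatment term appears. The fixed-effects line is not tied by name to one model, but time and a patient random effect fit only the repeated-measures analysis.

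For the secondary outcome the same section specifies "Percussion pain: ANCOVA with preoperative pain as covariate".

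Three other places bear on which scores are outcome rows. The objective and the null hypothesis concern postoperative pain. Section 12 places pain assessment on Days 1 to 7 after the procedure. Section 9 says that percussion pain too is assessed before and after the operation, and Section 10 then uses preoperative pain as a covariate.

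**The concern.** Two things are left open in the primary analysis.

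First, the plan adjusts the secondary outcome for a preoperative value and leaves the primary outcome unadjusted, although the score needed is already collected. If pre-operative spontaneous pain predicts later pain, precision is given away in a comparison of 40 against 40.

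Second, Section 9 lists the pre-operative record together with the daily ones, so an analyst could code it as the first level of time. With no time-by-treatment term, the model would then impose one treatment difference on all eight rows. One of those rows precedes treatment, and randomisation makes its expected difference zero. Both main effects would be pulled towards zero. That matters for the expected cryotherapy benefit in Section 13, and also for the expectation there that the two medicaments perform alike, which a shrunken contrast would flatter.

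The two codings give different primary estimates, and the choice could be made after the data are seen.

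**Working it through.** **Inputs from the plan.** Section 5: f = 0.40, power 0.90, alpha 0.05 (taken as two-sided), 80 patients, 20 per group. Section 3: "Randomized, double-blind, 2×2 factorial clinical trial", so each factor compares 40 with 40. For a two-level factor d = 2f = 0.80.

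**Assumptions, not in the documents.** Equal SD (set to 1) at every time; correlation 0.5 between any two post-operative days; correlation r between the pre-operative score and each post-operative day; a constant effect D on Days 1-7; complete data; a patient random intercept.

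**The plan's own figure.** Section 5 does not name the test. With noncentrality N × f² = 80 × 0.16 = 12.8, a one-degree-of-freedom factorial main effect (76 error df) has power 0.942 at N = 80, and 0.90 needs only 68. A three-degree-of-freedom test of four groups has power 0.845 at N = 80, and 0.90 needs 93 (96 in equal groups). The stated 80 is therefore not reproduced by either. That is a separate matter; the main-effect test is used below.

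**Method.** With balanced, complete data the random-intercept estimate of a main effect is the difference in patient means. Its noncentrality is (expected difference)² × 20 / V, where V is the variance of a patient mean and 20 = 40/2.

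- *A. Days 1-7, unadjusted:* V = (1 + 6 × 0.5)/7 = 0.571; expected difference D.
- *B. Pre-operative score as an eighth row:* expected difference (7 × D + 1 × 0)/8 = 7D/8, a 12.5% shrinkage whatever r is; V = (1 + 49 × 0.571 + 14r)/64.
- *C. Days 1-7 with pre-operative covariate:* V = 0.571 − r²; expected difference D; 75 error df.

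**Variance saved by the covariate (C against A), r²/0.571.** r = 0.1: 0.01/0.571 = 1.8%. r = 0.2: 0.04/0.571 = 7.0%. r = 0.3: 0.09/0.571 = 15.8%. r = 0.5: 0.25/0.571 = 43.8%.

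**Power at the plan's effect size.** Taking d = 0.80 on the patient-mean scale, D = 0.80 × √0.571 = 0.605.

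| r | V in B | V in C | Power A | Power B | Power C |
|---|---|---|---|---|---|
| 0.2 | 0.497 | 0.531 | 0.942 | 0.912 | 0.956 |
| 0.3 | 0.519 | 0.481 | 0.942 | 0.900 | 0.970 |
| 0.5 | 0.563 | 0.321 | 0.942 | 0.876 | 0.997 |

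If d = 0.80 is instead read on the single-day SD scale (D = 0.80), power is 0.997 for A, 0.985-0.992 for B and 0.998 or more for C.

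**A smaller effect, for sensitivity.** With D = 0.5, A has 0.832. B has 0.782, 0.765 and 0.731, and C has 0.857, 0.889 and 0.973, at r = 0.2, 0.3 and 0.5. At r = 0.1, C has 0.838. At r = 0, C and A agree to three decimals (0.832), so the covariate costs essentially nothing even if it is uninformative.

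**Check of the shrinkage.** In 100 simulated trials with all correlations 0.5 and a true effect of −0.60, fitted as mixed models, the mean estimates were −0.59 (A), −0.52 (B) and −0.58 (C); 7/8 × −0.60 = −0.525.

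**The case against.** The strongest reply is that an unadjusted mixed model on Days 1-7 is a valid analysis of a randomised trial. It is unbiased, and its standard error already allows for chance baseline imbalance, so adjustment is a choice about efficiency. That stands. The gain depends on a correlation that the documents do not give: at r = 0.1 it is under 2% of the variance. The 44% figure needs the pre-operative score to track each later day as closely as the later days track one another, although treatment comes in between.

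A reader might infer from Section 9 that the pre-operative score is meant to be an outcome row, and hence that the primary analysis as planned is biased towards zero. The documents do not support that. The outcome is named as postoperative pain, Section 12 points to Days 1-7, and the parallel percussion wording describes when scores are taken, with the earlier one used as a covariate. The text permits the eight-row coding but does not call for it. Shrinkage also needs the absence of a time-by-treatment term.

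A reader might also infer a serious loss of power from the 0.5 SD example. At the effect the trial was planned for, the eight-row coding still has about 0.88 or more against a target of 0.90, and the Days 1-7 analysis exceeds the target.

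**Conclusion.** The point holds as an omission and an ambiguity in the primary analysis. Bias is not established. The omission is plain: no pre-operative covariate is listed for spontaneous pain, and one is for percussion pain. Under the better-supported Days 1-7 reading, the cost is precision only, with a variance saving of about 2% to 44% forgone for r from 0.1 to 0.5. Under the eight-row reading, both main effects shrink by 12.5%; power at f = 0.40 is about 0.88-0.91, against 0.94 for Days 1-7 unadjusted and 0.96 or more with the covariate (r from 0.2 to 0.5).

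The factor 7/8 rests on complete data, a random intercept and no time-by-treatment term, with D as the effect averaged over Days 1-7. The power figures rest also on the assumed correlations, equal SDs and d = 0.80 on the patient-mean scale. This should be fixed, as an improvement that is essentially free; it does not invalidate the trial.

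**What to change.** In Section 10, state that the outcome rows of the spontaneous-pain model are Days 1-7 only, and add pre-operative spontaneous VAS as a fixed covariate, in line with the percussion ANCOVA. A baseline-by-day term may be added if the influence of the pre-operative score is expected to fade over the week.

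The cost is one sentence in the analysis plan and one degree of freedom for the covariate (more if the baseline-by-day term is added). The score is already collected, and neither the sample size nor the visit schedule changes. The wording should be settled before the data are analysed, so that the role of the pre-operative score cannot depend on the results.

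### The spontaneous-pain model has no treatment-by-time term, so it can neither test nor show an early, short-lived effect and averages any such effect down

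*Combined protocol and SAP*

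**What the plan says.** Section 9 defines the primary outcome as "Postoperative spontaneous pain (VAS 0–100 mm), recorded pre-op and daily for 7 days". Section 12 repeats the follow-up schedule as "Pain assessment: Days 1–7 postoperatively".

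Section 10 assigns this outcome a linear mixed model ("Spontaneous pain: Linear mixed-effects model for repeated measures") and gives its terms as "Fixed effects: Time, cryotherapy, medicament type, and cryotherapy \times medicament interaction" and "Random effect: Patient". These two lines come after the ANCOVA for percussion pain, but time and a random patient effect can only belong to the mixed model.

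No section adds a treatment-by-time term, a day-specific contrast or a primary day. The null hypothesis in the objectives is "No significant difference exists in postoperative pain among the study groups", and Section 13 says "Intracanal cryotherapy expected to reduce postoperative pain"; neither names a time. Section 10 makes pre-op pain a covariate for percussion pain only. For spontaneous pain it does not say whether the pre-op score is a covariate, a level of time, or left out.

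**The concern.** With time as a main effect only, the model fits parallel profiles. The cryotherapy difference is the same number on day 1 and on day 7, and with complete data its estimate is the plain average of the daily differences. This is a property of the model and needs no clinical assumption.

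Two things are at stake. First, the trial collects seven daily scores, yet the specified analysis cannot say whether a difference is early, late or sustained; any day-by-day comparison reported later would lie outside the plan. Second, a difference confined to the first days is averaged with days on which there is none. Section 8 describes cryotherapy as a single final rinse over 5 minutes, so a fading effect is worth guarding against, although the documents do not predict one.

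Baseline adds to the problem. If the pre-op score is a level of time, the model also requires the treatment difference to be present before treatment, which dilutes the estimate further.

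**Working it through.** **The plan's own figure.** Section 5 gives f = 0.40, power 0.90, α = 0.05 and 80 patients. By noncentral F, a 1-df test needs 68 patients (power 0.942 at 80). The 3-df four-group test needs 93, or 96 in equal groups (power 0.845 at 80). So 80 is not reproduced from the stated inputs. That is a separate matter, and nothing below depends on it. For a two-level factor d = 2f = 0.80, which is why 0.8 SD is used here.

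**Inputs.** From the plan: 80 patients, hence 40 v 40 for each factor; 7 post-operative days; α = 0.05. Assumed: effect of 0.8 SD on days 1–3 and none afterwards; the same within-patient correlation ρ between any two times, 0.3 to 0.7; complete data. Daily SDs are taken either as equal or as falling (25, 20, 15, 12, 10, 7, 5 mm; 25 mm pre-op).

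**Method.** With complete data, the planned test compares patient means. Let d be the mean difference divided by the SD of a patient mean. Power comes from the noncentral F on 1 and 76 df with λ = 80 × (d/2)².

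- Equal SDs, 7 days: difference 3 × 0.8/7 = 0.343 SD; SD of the mean = √((1 + 6ρ)/7).
- Equal SDs, pre-op included: 2.4/8 = 0.300 SD; √((1 + 7ρ)/8).
- Falling SDs, 7 days: 0.8 × (25 + 20 + 15)/7 = 6.86 mm; SD of the mean = √((1 − ρ)Σs² + ρ(Σs)²)/7, with Σs = 94 and Σs² = 1568. At ρ = 0.5 this is √(784 + 4418)/7 = 10.30 mm, so d = 0.67.
- Falling SDs, pre-op included: 48/8 = 6.00 mm; Σs = 119, Σs² = 2193. At ρ = 0.5 this is √(1096.5 + 7080.5)/8 = 11.30 mm, so d = 0.53.

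| Days 1–3 effect, power of the average | ρ = 0.3 | ρ = 0.5 | ρ = 0.7 |
|---|---|---|---|
| Equal SDs, 7 days | 67% | 52% | 42% |
| Equal SDs, pre-op as a level of time | 57% | 42% | 34% |
| Falling SDs, 7 days | 93% | 84% | 74% |
| Falling SDs, pre-op as a level of time | 80% | 65% | 54% |

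**Other time courses, equal SDs, 7 days.** A constant 0.8 SD gives 98% or more at every ρ. An effect on day 1 only averages 0.8/7 = 0.11 SD and has power 13% to 9%.

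**What a cryotherapy-by-day test would add.** With equal SDs, λ = (80/4) × Σ(dⱼ − d̄)²/(1 − ρ) on 6 and 456 df, where dⱼ is the effect on day j and d̄ its mean over days. For the days 1–3 effect at ρ = 0.5, Σ = 3 × 0.457² + 4 × 0.343² = 1.10 and λ = 20 × 1.10/0.5 = 44. Power is over 99% at every ρ. For day 1 only it runs from 86% to over 99%.

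**The case against.** **The 7-day average is a legitimate target.** It fits a null hypothesis without a time point and an outcome recorded daily for a week. The medicament stays sealed in the canal, so the single-rinse argument does not apply to that factor. This stands: the average need not be abandoned. It does not explain why the model offers no means of checking whether the effect changes over the week.

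**A reader might infer that the primary test will probably miss a real early effect.** The documents do not support that. They give no time course, and the 52% figure needs equal SDs on all days. If SDs fall with the pain, quiet late days shrink the average but add little noise, and the same scenario gives 84%.

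**A reader might also infer that the random intercept invalidates the test, because daily SDs are unlikely to be equal.** With the assumed falling SDs, the pooled SD is √(1568/7) = 14.97 mm. A day-1 comparison using it would have a true error rate of 2 × (1 − Φ(1.96 × 14.97/25)) = 24%. But the plan contains no day-1 comparison. Both treatments vary between patients, so with complete data the planned test is a comparison of patient means, whatever the daily SDs. In 20,000 simulated trials with these SDs, ρ = 0.5 and no effect, that comparison rejected 4.9% of the time. Unequal variance matters only once day-specific effects are estimated.

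**A reader might conclude that days 1–3 must become the primary contrast.** That is a choice of estimand and can be costly. For a constant 8 mm effect (assumed) with the falling SDs and ρ = 0.5, power is 93% for the 7-day mean and 58% for the days 1–3 mean.

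**Conclusion.** The point holds in a limited form. On the listed terms, the primary model imposes one constant treatment effect over all recorded times. It cannot test or display a change over time, and it averages an early effect down. That much follows from Section 10 alone.

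The size of the loss rests on assumptions. In the days 1–3 scenario, power is 42–67% with equal SDs and 74–93% with falling SDs, or 34–57% and 54–80% if pre-op pain is a level of time. If the effect is constant at 0.8 SD, there is no material loss. With complete data, the error rate of the planned average test is sound. This should be fixed, but it does not invalidate the primary test.

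**What to change.** Rewrite the spontaneous-pain entry in Section 10 as follows:

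- Responses are the post-operative scores on days 1–7, with day as a categorical factor.
- Keep cryotherapy, medicament and their interaction; add day × cryotherapy and day × medicament.
- Pre-op spontaneous pain enters as a covariate, not as a level of time.
- Use a within-patient covariance that lets the SD differ by day: unstructured, with a named simpler structure as fallback if the model does not converge.
- State before unblinding one primary contrast for cryotherapy: the 7-day post-operative mean, or an early window if the sponsor justifies it.
- Report the cryotherapy-by-day test and the day-specific estimates as pre-specified secondary results.

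No extra patients or visits are needed. The cost is model size with 80 patients: 2 × 6 = 12 further interaction parameters, and 7 × 8/2 = 28 covariance parameters in place of 2. That is why the fallback has to be written down in advance.

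### Only pain scores are collected after treatment, so the trial will have no data by arm on flare-up, re-treatment or other adverse events

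*Combined protocol and SAP*

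**What the plan says.** The primary outcome in Section 9 is "Postoperative spontaneous pain (VAS 0–100 mm), recorded pre-op and daily for 7 days". The secondary outcome is also a pain VAS, on percussion. Section 12 lists one follow-up activity: "Pain assessment: Days 1–7 postoperatively".

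Swelling and abscess appear once, in the Section 6 exclusion list: "Acute apical abscess or swelling". Section 8 closes the procedure with "Temporary restoration of access cavity", so the medicament is meant to stay sealed in the canal.

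Section 10 fits a mixed model to the repeated scores. It contains no safety analysis and no rule for scores given after unscheduled treatment of the tooth. Section 11 has the one related rule: the pain score is to be given ahead of any painkiller. Section 13 anticipates "Metformin effect on short-term pain expected to be comparable to calcium hydroxide".

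**The concern.** The patients have necrotic premolars with a medicament sealed in, half of them with metformin and half after a cold rinse. The plan treats swelling and abscess as serious enough to keep a patient out, then does not ask whether either occurs after treatment.

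Two things are at stake. First, the trial would have no comparison of harm. It could meet its expectation on metformin and pain while being unable to say whether flare-up or re-treatment was more common with one medicament, or with or without cryotherapy. Analysts could not fill that gap reliably afterwards.

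Second, a tooth that is re-opened during the week continues to yield VAS scores. Under Section 10 as written, these enter the model under the allocated arm, and no data would show which scores they are. A reader could not tell whether they matter.

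**Working it through.** **Is the gap real?** Setting the sections side by side:

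- Section 6: swelling and abscess, at entry only.
- Section 9: two outcomes, both pain VAS.
- Section 10: models for the two pain outcomes only.
- Section 11: score timing relative to painkillers; silent on re-treatment.
- Section 12: pain on Days 1–7.

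No section provides for recording a post-treatment event, so the gap is confirmed.

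**Inputs.** From Section 5: 80 patients, 20 per group, hence 40 at each level of each factor. The plan gives no flare-up rate, VAS level, VAS drop or SD, so there is no figure of its own to reproduce on this point. How the 80 was reached does not affect it. Everything below marked as assumed is illustration.

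**Are events likely to arise?** The chance of at least one event is 1 − (1 − p)^n:

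| Assumed rate p | n = 20 | n = 40 | n = 80 |
|---|---|---|---|
| 2% | 33% | 55% | 80% |
| 5% | 64% | 87% | 98% |
| 10% | 88% | 98.5% | over 99% |

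**What would recording them show?** With zero events, the one-sided 95% upper bound is 1 − 0.05^(1/n): 13.9% for n = 20, 7.2% for n = 40, 3.7% for n = 80. The two-sided exact 95% interval for zero in 40 reaches 1 − 0.025^(1/40) = 8.8%.

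Power for a two-sided 5% comparison of two proportions, n per level, is Φ[(|p1 − p2| − 1.96·√(2p̄(1 − p̄)/n)) / √((p1(1 − p1) + p2(1 − p2))/n)]. For an assumed 5% versus 15% with n = 40: (0.10 − 1.96 × 0.0671)/0.0661 = −0.476, power about 32%. For 5% versus 20%, about 53%. The outcome is therefore descriptive.

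**Does re-treatment bias the pain comparison in a known direction?** Assume a patient scores 70 mm before re-opening and 15 mm after.

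- Re-opened after the Day 1 score: 7-day mean (70 + 6 × 15)/7 = 22.9 mm.
- Re-opened after the Day 2 score: (2 × 70 + 5 × 15)/7 = 30.7 mm.

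Such a patient lowers the arm's mean only if patients without flare-up average more than that. If they average 15 mm, a 10% flare-up rate raises the arm's mean, by 0.10 × (22.9 − 15) = 0.8 mm or 0.10 × (30.7 − 15) = 1.6 mm. Without VAS levels in the plan, the sign is unknown.

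Against a hypothetical course that stays at 70 mm through Day 7, the mean is lower by rate × share of days × 55 mm. At 10% this is 0.10 × (6/7) × 55 = 4.7 mm, or 0.10 × (5/7) × 55 = 3.9 mm. Over 5% to 15% the range is 2.0 to 7.1 mm. That is a penalty only partly counted, not an advantage shown.

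**The case against.** The strongest reply is that keeping every observed score under the allocated arm is an ordinary treatment-policy analysis, so nothing is biased by construction. This stands. The plan's fault is that it neither states this choice nor collects what is needed to examine it.

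A reader might go further and infer that the primary outcome favours whichever arm has more flare-ups. The documents do not support that: high scores before re-treatment still count against the arm, and the net effect can go either way. The same reader might set the 2.0 to 7.1 mm shortfall against the planned effect. With f = 0.40 on a two-level factor, d = 0.8. An assumed SD of 15 mm makes this 12 mm, and the shortfall 16% to 59% of it. At an SD of 25 mm it is 20 mm, and 10% to 35%. These ratios also need all the flare-ups to fall at one factor level (at 10%, 4 of 40 against 0 of 40). They rest wholly on assumed values and are not a finding.

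Three other readings also fail. Relieved scores do not count as success, since the endpoint is a continuous VAS with no success threshold. Stopping at Day 7 is a declared scope choice, listed as a limitation in Section 14. Section 13 already confines its expectation of comparability to short-term pain.

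It may also be said that routine clinic notes would hold such events. They may, but the plan does not provide for extracting or reporting them.

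**Conclusion.** The omission holds on the text. Post-treatment collection is limited to pain VAS, and the trial as written would yield no counts of flare-up, re-treatment or other adverse events for either factor. Its conclusions on metformin and cryotherapy would have to stop at pain. Whether scores after re-treatment affect the pain comparison could not be checked, and no direction or size can be given from the documents.

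The omission itself rests on no assumption beyond the documents' silence. The event probabilities depend on assumed rates; the zero-event bounds depend only on the planned numbers of patients. This is a cheap improvement to what is collected and what can be concluded, and does not invalidate the pain analysis.

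**What to change.** - **Sections 9 and 12:** add a descriptive secondary safety outcome. Define flare-up as new swelling or abscess, an unscheduled visit for the study tooth, or re-opening or loss of the medicament, and add any other adverse event. Collect it through a dated yes/no item with the daily VAS on Days 1–7, and from the clinic record.
- **Reporting:** give counts by cryotherapy and by medicament, with differences and exact 95% confidence intervals.
- **Section 10:** state that the mixed model on all observed scores is the primary, treatment-policy analysis. Add one sensitivity analysis that sets VAS after re-intervention to missing, and state that it assumes those values are missing at random given the scores already recorded.

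The cost is one extra item for patients, a check of clinic records, one table and one further model run, with no extra patients, staff or procedures. The intervals will be wide, and the text should say so. How flare-ups are managed clinically is left to the sponsor.
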